9.4.7.2 Prohibited Concomitant Therapies and Drugs

The following treatments are prohibited while on this study:

- No other investigational therapy should be given to subjects. No anticancer agents other than the study medications should be given to subjects. If such agents are required for a subject, then the subject must first be withdrawn from the study.
- In vitro, H3B-6545 is a reversible and time-dependent inhibitor of CYP2C8, 2C9, 2C19, and CYP3A4, as well as an inhibitor of the BCRP, multidrug and toxin extrusion transporter (MATE)1, MATE2-K, organic anion transporting polypeptide (OATP)1B1, and P-gp mediated transport. Drugs with narrow therapeutic index and known to be metabolized by CYP2Cs or CYP3A4 are not permitted because of the inherent potential risk of either reduced activity or enhanced toxicity of the respective concomitant medication (and/or inhibition of P-gp). Medications that are strong inducers or inhibitors of CYP3A or P-gp should also be avoided since H3B-6545 is a substrate of P-gp and mainly metabolized by CYP3A4, followed by 3A5 and 2C8, and palbociclib is also mainly metabolized CYP3A. For the most updated information, visit the following Web address: http://medicine.iupui.edu/clinpharm/ddis/. Histamine H₂-receptor antagonists.
- Because of a potential DDI, BCRP substrates with narrow therapeutic index are not permitted because H3B-6545 is an inhibitor of BCRP (but not a substrate) (Appendix 1)
- If, after a subject has been enrolled, she requires the concomitant use of any of the medications that may cause QTc interval prolongation, then H3B-6545 must be held while the subject receives the concomitant medication. Resumption of treatment with H3B-6545 may be considered following discontinuation and washout (at least 5 half-lives) of the concomitant medication if the subject has not progressed and is agreed upon with the sponsor. Excluded medications that may cause QTc interval prolongation are also listed and updated at the following Web address: http://crediblemeds.org.
- Herbal preparations/medications are not allowed throughout the study. These herbal medications include, but are not limited to, St. John's wort, kava, ephedra (ma huang),

gingko biloba, dehydroepiandrosterone, yohimbe, saw palmetto, and ginseng. Subjects should stop using these herbal medications 7 days prior to the first dose of the study drug.

- Nutritional supplements, juice, other foods, or beverages that may affect the various drug-metabolizing enzymes and transporters (eg, alcohol, grapefruit, grapefruit juice, grapefruit-containing beverages) are not allowed for 1 week before and throughout the study.
- Systemic corticosteroids are not allowed during the study. Note: The following uses of corticosteroids are permitted: single doses, topical applications (eg, for rash), inhaled sprays (eg, for obstructive airway diseases), eye drops, or local injections (eg, intraarticular). Short courses of systemic corticosteroids may be considered in consultation with the medical monitor.
- Use of short course palliative radiotherapy for symptomatic isolated bone metastases may be allowed following discussion with sponsor.

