9.3.3 Removal of Subjects From Therapy or Assessment

Subjects will continue to receive study treatment until any of the following occur:

• Disease progression

- Development of unacceptable toxicity. In absence of liver metastases at baseline and in absence of clinical or radiological evidence of biliary obstruction: ALT or AST >3 × ULN, in conjunction with total bilirubin >2 ×ULN
- Withdrawal of consent
- Subject request
- Inability to comply with protocol requirements

The reason for treatment discontinuation will be documented. If a subject discontinues study treatment, the subject will enter the Follow-Up Period and complete protocol-specified off-treatment visits, procedures, and survival follow-up unless the subject withdraws consent. The investigator should confirm whether a subject will discontinue trial therapy but agree to continue protocol-specified, off-treatment study visits, procedures, and survival follow-up, or whether the subject will withdraw consent. If a subject withdraws consent, the date will be documented in the source documents.

During the Follow-Up Period, subjects who have discontinued study treatment without progression will be followed for disease assessments every 8 weeks from the date of the last assessment until the data cutoff date for the primary analysis, or until disease progression is documented or another anticancer therapy is initiated. Subjects will be followed for AEs for 28 days after the last treatment administration. Subjects who discontinue 1 of the 2 drugs and continue therapy with the other one are considered *on treatment* until they discontinue the 2nd drug.

All subjects will be followed for survival until death approximately every 3 months for up to 6 months after the last subject receives their first dose of study treatment (ie, primary analysis data cutoff date), except where a subject withdraws consent or the sponsor chooses to halt survival follow-up.

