9.6.4.3 Reporting of Pregnancy and Exposure to Study Drug Through Breastfeeding

Any pregnancy in a female subject in which the estimated date of conception is either before the last visit or within 28 days of last study treatment, or any exposure to study drug through breastfeeding during study treatment or within 28 days of last study treatment, must be reported.

If an adverse outcome of a pregnancy is suspected to be related to study drug exposure, this should be reported regardless of the length of time that has passed since the exposure to study treatment.

A congenital anomaly, death during perinatal period, a spontaneous abortion or an induced abortion done due to safety concerns for either mother or fetus are considered to be an SAE

and should be reported in the same time frame and in the same format as all other SAEs (see Reporting of Serious Adverse Events [Section 9.6.4.2]).

Pregnancies or exposure to study drug through breastfeeding must be reported by fax or email as soon as possible but no later than 24 hours from the date the investigator becomes aware of the pregnancy. The contact information for the reporting of pregnancies and exposure to study drug through breastfeeding is provided in the Investigator Study File. The Pregnancy Report Form must be used for reporting. All pregnancies must be followed to outcome. The outcome of the pregnancy must be reported as soon as possible but no later than 24 hours from the date the investigator becomes aware of the outcome.

A subject who becomes pregnant must be withdrawn from the study.

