9.6.5 Completion/Discontinuation of Subjects

The investigator may discontinue study drug for a subject at any time for safety or administrative reasons. A subject may elect to discontinue trial therapy or withdraw consent for further participation in the study at any time for any reason. All subjects who withdraw consent for further participation in the study are to complete the study's early discontinuation procedures indicated in the Schedule of Procedures/Assessments (Table 8).

Subjects will be discontinued from study treatment for any of the following reasons:

- Disease progression*
- Irreversible or intolerable toxicity or abnormal laboratory values thought to be related to drug toxicity
- Conditions requiring therapeutic intervention not permitted by the protocol
- Intercurrent illness (at the investigator's discretion)
- Inability of the subject to comply with study requirements, or subject is lost to follow-up
- Subject requests to discontinue treatment
- Subject withdraws consent from the study
- Pregnancy

*Subjects may continue to receive treatment after progression only if, after discussion with the medical monitor, it is determined that the subject continues to derive clinical benefit.

After discontinuation from protocol treatment, subjects must be followed for AEs for 28 days after their last dose of study drug. All new AEs, including SAEs, occurring during this period must be reported and all SAEs must be followed until resolution, unless, in the opinion of the investigator, these events are not likely to improve because of the underlying disease. In this case, the investigator must record his or her reasoning for this decision in the

subject's medical records and indicate on the AE pages that the outcome is not resolved on the electronic case report form (eCRF).

All subjects who have Grade 3 or 4 laboratory abnormalities (per NCI CTCAE v5.0) at the time of discontinuation must be followed until the laboratory values have returned to Grade 1, 2, or baseline for the subject, unless it is, in the opinion of the investigator, not likely that these values are to improve. In this case, the investigator must record his or her reasoning for making this decision in the subject's medical records and indicate on the AE pages that the outcome is not resolved on the eCRF.

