5.4.2 Secondary Efficacy Analyses

ORR and CBR will be summarized by treatment groups, and exact 95% CIs will be provided using the method of Clopper and Pearson (1934).

In addition, waterfall plot of best percentage change of sum of diameters in target lesion will be provided for RES subjects

PFS analysis will follow the FDA censoring rule guidance: progression date is assigned to the earliest date when any RECIST 1.1-defined disease progression is observed without missing more than 1 adequate radiologic assessments. Details are included in Appendix 13.2. The distribution of PFS will be estimated using Kaplan-Meier methodology. Median PFS and the corresponding 2-sided 95% CIs (Brookmeyer and Crowley, 1982) will be summarized by treatment groups. The PFS rate at 3-month, 6-month, and 9-month and 12-month will be estimated using the Kaplan-Meier Method and the corresponding 2-sided 95% CIs will be summarized. In addition, Kaplan-Meier plots of PFS will be presented.

DOR will be calculated for subjects achieving a best overall response of confirmed PR+CR. If there are ≥7 subjects with confirmed responses, the median of DOR will be estimated using Kaplan-Meier methodology; median DOR and the corresponding 2-sided 95% CI will be presented by treatment groups on RES. The same logics in censoring rules as those for PFS analysis will be applied. If there are <7 subjects with confirmed responses, DOR will be listed.

OS will be censored at the last alive date or data cutoff date, whichever comes first. The distribution of OS will be estimated using Kaplan-Meier methodology. Median survival time and the corresponding 95% CI, survival rates at 6, 12, 18, 24 months, and corresponding 95% CIs will be estimated using Kaplan-Meier method. The analysis will be presented by treatment groups.

Eisai Confidential Page 14 of 30

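### The prohibited-therapy rule says a subject who needs another anticancer agent is withdrawn from the study, which conflicts with the sections that keep such subjects in survival and safety follow-up

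*Protocol*

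**What the plan says.** **The rule.** Protocol Section 9.4.7.2, on prohibited concomitant therapies, bars anticancer agents other than the study drugs and adds: "If such agents are required for a subject, then the subject must first be withdrawn from the study". The Synopsis repeats this sentence.

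**The same situation elsewhere.** Section 9.6.5 lists reasons for stopping study *treatment*. One is "Conditions requiring therapeutic intervention not permitted by the protocol"; pregnancy is another. It then requires 28 days of adverse event (AE) follow-up after the last dose.

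**Follow-up after stopping treatment.** Under Section 9.3.3, a subject who stops treatment is to "complete protocol-specified off-treatment visits, procedures, and survival follow-up unless the subject withdraws consent". It continues: "All subjects will be followed for survival until death approximately every 3 months", up to the primary analysis cutoff, "except where a subject withdraws consent or the sponsor chooses to halt survival follow-up". Section 9.1.3 and Table 8 footnote a also apply survival follow-up to all subjects. Footnote u says so specifically for the time after progression.

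**Analysis.** SAP Section 5.4.2 states: "OS will be censored at the last alive date or data cutoff date, whichever comes first". It reports survival rates at 6, 12, 18 and 24 months.

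**Pregnancy.** Section 9.6.4.3 uses the same kind of wording, "A subject who becomes pregnant must be withdrawn from the study", yet requires every pregnancy to be followed to its outcome.

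**The concern.** Stopping study drug and leaving the study have different consequences. After stopping study drug, a subject still contributes survival and safety data; after leaving the study, she does not. Section 9.3.3 makes this distinction and asks the investigator to confirm which applies. The bullet in Section 9.4.7.2 blurs it.

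The trigger is not rare, since many subjects with progression will need another anticancer agent. If a site records such a subject as withdrawn and stops calling, her last known alive date falls near the start of next therapy and the SAP censors her there. Subjects leave the risk set just as their risk of death rises, so the censoring is informative and Kaplan-Meier OS is too high. The trial has about 7 sites and 12 to 24 escalation subjects, and the SAP says no expansion subjects will be enrolled. A few cases could therefore move the curve.

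**Working it through.** **1. Text comparison.** The plan states no figure that could be reproduced here, so the first check is what the start of another anticancer agent ends in each place.

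| Place | What it ends |
|---|---|
| Protocol 9.4.7.2 and Synopsis | Study participation (must precede the new agent) |
| Protocol 9.6.5 (non-permitted therapy) | Study treatment only |
| Protocol 9.1.3, 9.3.3, 9.6.1.2.1 | Tumor assessments only |
| Protocol 9.6.1.4.1 | Follow-to-resolution of an existing AE |
| Protocol 9.3.3, survival follow-up | Nothing; only consent withdrawal or a sponsor halt ends it |
| SAP 13.2 (PFS) | PFS follow-up, by censoring |
| SAP 5.4.2 (OS) | Nothing; censored at last alive date or cutoff |

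Only the first row ends survival follow-up. The SAP's OS rule assumes that contacts continue after next therapy.

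**2. Size if the bullet is applied literally.**

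Input from the documents: median PFS 5.3 months, the monotherapy figure in Protocol 7.2.1.

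Assumptions not in the documents:
- times are exponential;
- 5% of PFS events are deaths;
- median survival after progression is 9, 15 or 24 months;
- a fraction *q* of progressing subjects, unrelated to prognosis, start a new agent at progression and are withdrawn then.

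Formulas, with *t* in months:
- λ₁ = ln 2 / 5.3 = 0.1308; λ₂ = ln 2 / 9, 15 or 24 = 0.0770, 0.0462 or 0.0289
- Progression-free: P(t) = exp(−λ₁t), so P(12) = 0.208
- Alive after progression: A(t) = 0.95 · λ₁/(λ₁ − λ₂) · [exp(−λ₂t) − exp(−λ₁t)], so A(12) = 0.436, 0.538 or 0.608
- True OS(12) = P(12) + A(12) = 0.644, 0.746 or 0.816
- Hazard seen by Kaplan-Meier: h(t) = [0.05·λ₁·P + (1−q)·λ₂·A] / [P + (1−q)·A]; apparent OS(12) = exp(−∫₀¹² h dt)
- For q = 1: exp(−0.05 × 0.1308 × 12) = exp(−0.0785) = 0.925

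12-month OS (increase over true, in percentage points):

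| Median after progression | True | q = 1/4 | q = 1/2 | q = 1 (upper bound) |
|---|---|---|---|---|
| 9 months | 64.4% | 67.7% (+3.3) | 72.4% (+8.0) | 92.5% (+28.1) |
| 15 months | 74.6% | 76.7% (+2.1) | 79.7% (+5.1) | 92.5% (+17.9) |
| 24 months | 81.6% | 82.9% (+1.3) | 84.7% (+3.1) | 92.5% (+10.9) |

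These are large-sample values; sampling error with 24 or fewer subjects comes on top.

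**3. Who remains under OS follow-up at q = 1.** The share is about 0.5^(t/5.3): 46%, 21%, 9.5% and 4.3% at 6, 12, 18 and 24 months. That is about 11, 5, 2 and 1 of 24 subjects, before any cutoff censoring. For assumed PFS medians of 4 to 12 months, the ranges are 35–71%, 13–50%, 4–35% and 2–25%.

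**4. AE collection.** Sections 9.6.1.4.1, 9.6.4.2 and 9.6.5 require AE or serious AE collection for 28 days after the last dose, with no exception for new therapy. The bullet could shorten this only for a subject whose new agent starts inside those 28 days.

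**The case against.** The strongest reply is that the bullet concerns concomitant use. It sits under concomitant therapy, so its natural target is a subject still on study drug. A progressing subject normally stops because of progression and is then governed by the follow-up sections, which are specific and repeated. The SAP points the same way: its PFS rules provide for new treatment before death, and Section 5.6.3 tabulates deaths after study treatment. Section 9.6.4.3 also uses study withdrawal loosely for pregnancy. This stands as evidence of intent and makes a literal reading less likely. It does not remove the contradiction, because the bullet makes withdrawal a condition of giving the new agent and carries no pointer to Section 9.3.3.

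It is also fair to say that the size rests on assumptions. Survival after progression, the 5% share of deaths and the fraction withdrawn are not in the documents, and 5.3 months comes from monotherapy.

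A reader might infer three stronger things, none of which the documents support:
- *The plan ends OS follow-up for subjects who progress.* It does not; Table 8 footnote u says the opposite. The bullet also misses progressing subjects who receive no further therapy.
- *28-day AE data are lost for the same subjects.* This needs a new agent inside the window and a site that disregards the AE sections.
- *12-month OS would read about 92%.* That requires every progressing subject to be withdrawn at progression.

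**Conclusion.** The contradiction is real and stands in two places, Section 9.4.7.2 and the Synopsis. The probable intent is withdrawal from treatment, so harm arises only where a site reads the bullet literally. The bias in OS is then upward, and its size depends on how many subjects are handled that way. Partial adherence (a quarter to a half) gives about 1 to 8 points at 12 months under the stated assumptions; the 11 to 28 points from withdrawing everyone is an upper bound, not an expectation.

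Severity is minor. OS is a descriptive secondary endpoint, its follow-up already ends at the primary cutoff, no formal sample size calculation is involved, and the determination of the MTD/RP2D is unaffected. The pregnancy wording is the same drafting fault and has no bearing on the OS bias.

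**What to change.** 1. Reconcile Section 9.4.7.2 and the Synopsis with Sections 9.3.3 and 9.6.5 and Table 8 footnote u, so that leaving study treatment is clearly separated from leaving the study. State that survival follow-up and 28-day AE collection continue after another anticancer agent starts, unless consent is withdrawn. Section 9.3.3's provision for a sponsor halt of survival follow-up can remain. The edit should change no rule on when treatment stops or resumes.
2. Reconcile the pregnancy sentence in Section 9.6.4.3 with Section 9.6.5 in the same way.
3. Send sites a short clarification.
4. Before database lock, identify any subject recorded as withdrawn for this reason and check her survival status up to the cutoff, where consent allows.

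The cost is three wording edits, one site clarification and a status check for any affected subjects. No visit is added beyond those already planned.

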9.4.7.3 Permitted Concomitant Medications

No routine prophylactic antiemetic is required. However, the use of palonosetron, prochlorperazine, promethazine, and cyclizine for management of nausea and vomiting is allowed. The use of ondansetron and granisetron is not permitted because of their potential to prolong QT interval.

Medications may be administered for maintenance of existing conditions prior to study enrollment or for a new condition that develops while on study, including but not limited to the following:

- Growth factors: Prophylactic use of GCSF is not allowed from Cycle 1 Day 9 to Cycle 2 Day 8. Subjects receiving recombinant erythropoietin or darbepoietin-α prior to study start may continue to receive pretreatment doses. Following initiation of study treatment, the use of erythropoietic and granulocyte growth factors in accordance with local practice or ASCO guidelines may be implemented at the discretion of the treating physician.
- Bisphosphonate use, as recommended according to practice guidelines as long as the subject has been on a stable dose for >30 days prior to study enrollment
- RANKL inhibitor use, as recommended according to practice guidelines, as long as the subject has been on a stable dose >30 days prior to study enrollment
- Anticoagulation with warfarin and derivatives will not be permitted. Should a thrombotic event occur while the subject is receiving treatment, the subject may continue, but low-molecular-weight heparin, dabigatran, or edoxaban will be the preferred treatment.
- Subjects who develop hyperglycemia during the study should be treated as determined by the treating clinician, according to the national diabetes management guidelines.

Other medications considered necessary for the subject's safety and well-being may be given at the discretion of the investigator with the exception of those listed in Section 9.4.7.2.

9.4.8 Treatment Compliance

Records of treatment compliance for each subject will be kept during the study. A diary will be provided to subjects on Cycle 1 Day 1 to document the date and time of each study drug dose for all treatment cycles as well as the incidence of vomiting following administration. The investigator will review and document treatment compliance for each subject at each visit. CRAs will review treatment compliance during site visits and at the completion of the study.

9.4.9 Drug Supplies and Accountability

In compliance with local regulatory requirements, the initial drug supply will not be sent to the investigator until local regulatory and IRB/IEC approvals are available, and all required forms and documentation have been reviewed by the sponsor:

- A signed and dated confidentiality agreement
- A copy of the final protocol signature page, signed and dated by both the sponsor and investigator
- Written proof of approval of the protocol, the ICFs, and any other information provided to the subjects by the IRB/IEC for the institution where the study is to be conducted
- A copy of the IRB/IEC-approved ICF and any other documentation provided to the subjects to be used in this study
- The IRB/IEC membership list and statutes or Health and Human Services Assurance number
- An investigator-signed and dated Food and Drug Administration (FDA) Form FDA 1572, or a completed Investigator and Site Information Form
- Financial disclosure form(s) for the PI and all subinvestigators listed on Form FDA 1572 or Investigator and Site Information Form
- A signed and dated curriculum vitae of the PI including a copy of the PI's current medical license or medical registration number on the curriculum vitae
- A signed and dated clinical studies agreement

The investigator and the study staff will be responsible for the accountability of all study drugs (dispensing, inventory, and record keeping) following the sponsor's instructions and adherence to GCP guidelines as well as local or regional requirements.

Under no circumstances will the investigator allow the study drugs to be used other than as directed by this protocol. Study drugs will not be dispensed to any individual who is not enrolled in the study.

The site must maintain an accurate and timely record of the following: receipt of all study drugs, dispensing of study drugs to the subject, collection and reconciliation of unused study drugs that are either returned by the subjects or shipped to site but not dispensed to subjects,

and return of reconciled study drugs to the sponsor or (where applicable) destruction of reconciled study drugs at the site. This includes, but may not be limited to: (a) documentation of receipt of study drugs, (b) study drugs dispensing/return reconciliation log, (c) study drugs accountability log, (d) all shipping service receipts, (e) documentation of returns to the sponsor, and (f) certificates of destruction for any destruction of study drugs/study supplies that occurs at the site. All forms will be provided by the sponsor. Any comparable forms that the site wishes to use must be approved by the sponsor.

The study drugs and inventory records must be made available, upon request, for inspection by a designated representative of the sponsor or a representative of a health authority. As applicable, all unused study drugs and empty and partially empty containers from used study drugs are to be returned to the investigator by the subject and, together with unused study drugs that were shipped to the site but not dispensed to subjects, are to be returned to the sponsor's designated central or local depot(s) during the study or at the conclusion of the study, unless provision is made by the sponsor for destruction of study drugs and containers at the site. Destruction at the site will only occur under circumstances where regulation or supply type prohibits the return of study drugs to the central or local depot(s). Approval for destruction to occur at the site must be provided by the sponsor in advance. Upon completion of drug accountability and reconciliation procedures by the site's personnel and documentation procedures by the sponsor's personnel, study drugs that are to be returned to the sponsor's designated central or local depot(s) must be boxed, sealed, and shipped back to the central or local depot(s) following all local regulatory requirements. In some regions, study drugs may be removed from the site and hand delivered to the central or local depot by sponsor representatives. Where study drugs are approved for destruction at the site, destruction will occur following the site's standard procedures and certificates of destruction will be provided to the sponsor.

Drug accountability will be reviewed during site visits and at the completion of the study.

